--	--

	
renal, neurological disorders (including demyelinating disease), active infectious diseases, endocrinological, gastrointestinal, hepatobiliary, metabolic, pulmonary (eg, severe asthma, cystic fibrosis), nonmalignant lymphoproliferative diseases, other lymphatic disease(s), autoimmune disease, psychiatric disorders, etc
 
 • Patients with nonhealed/healing skin ulcers • Surgery within 4 weeks prior to the Screening visit or with planned surgery during the course of the study • History of a systemic hypersensitivity reaction, other than localized injection site reaction, to any biologic drug and known hypersensitivity to any constituent of the product • History of inflammatory bowel disease, severe diverticulitis, or previous gastrointestinal perforation whatever the cause • Uncontrolled diabetes mellitus, defined as glycosylated hemoglobin (HbA1c) $\geq 9\%$ at the Screening visit • Conditions/situations such as: 
 - Patients with short life expectancy - Conditions/concomitant diseases making patients non-evaluable for the efficacy endpoints, eg, patients with chronic pain caused by conditions other than JIA, eg, fibromyalgia - Patients whose immediate family members are dependent (employee) of site/Investigator, and individuals who are institutionalized due to regulatory or legal order. • Any of the following laboratory abnormalities at the Screening visit (identified by the central laboratory): 
 ■ [REDACTED] ■ [REDACTED] ■ [REDACTED] ■ [REDACTED] ■ [REDACTED] ■ [REDACTED] ■ [REDACTED] ■ [REDACTED] ■ [REDACTED] ■ [REDACTED] ■ [REDACTED] • Pregnant or breast-feeding female adolescent patients (refer to main body of protocol for details).
Total expected number of patients	Assuming that 3 dose regimens will be tested and one of these 3 dose regimens will be selected, up to approximately 72 patients will be enrolled (to achieve approximately 60 evaluable patients) in the dose-finding and second portions. Approximately 28 additional patients will be enrolled in the third portion to achieve a total of approximately 100 treated patients for the entire study.
Expected number of sites	Approximately 45 sites (additional sites could be opened).
STUDY TREATMENT(s)	

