1.1.2 Study flow diagram

Abbreviations: EOS = end-of-study, EOT = end-of-treatment, PK = pharmacokinetic, V = visit, Wk = week

Notes: All patients must complete an end-of-treatment (EOT) visit (V27, Week 156 for dose-finding and second portions/Week 96 for third portion) at the completion of treatment (last IMP injection at Week 154/Week 94 for Dose Regimens 1 and 2 Cohorts and at Week 155 for Dose Regimen 3 Cohort) or at the time of early permanent treatment discontinuation (regardless of treatment phase).

For a patient who discontinues study treatment prematurely during the 12-week core treatment phase, interleukin-6 (IL-6) and soluble interleukin-6 receptor (sIL-6R) will be measured at EOT visit. For patients in the dose-finding and second portions who discontinue study treatment prematurely during 12-week core treatment phase, an additional PK visit, 2 weeks after the EOT visit is required for blood sampling (V88).

All patients must complete a post-treatment follow-up visit (V28) 6 weeks after the EOT visit. However, patients discontinuing treatment prematurely during the core treatment phase should continue to return for the study visits as protocol scheduled without treatment administration through Week 12 (as per Food and Drug Administration (FDA) guidelines for missing data).

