### 2.1.5 Efficacy endpoints

The primary endpoint for these studies is PK exposure, and efficacy endpoints are secondary. Efficacy assessment will be performed as described below.

The evaluation schedule for efficacy variables can be found in Section 1.2 Study Flow Charts of the protocols [REDACTED]

Note that all efficacy evaluations up to the closeout measurement will be included for analysis unless otherwise specified. Baseline for efficacy variables is defined as the last non-missing value on or before the date of inclusion (assigned treatment). For patients who have no value on or before the inclusion date, the last non-missing value on or before the date of first IMP intake will be used as baseline.

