### 2.1.5.2 Other secondary efficacy endpoint(s)

In addition to the assessment of responders as per the definition stated above, the other secondary efficacy endpoints for the 12-week core part are the change from baseline at week 12 in the 6 individual JIA ACR components, and JIA ACR30 response at week 12 using ESR instead of hs-CRP. Additional efficacy endpoints are listed as follows.

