#### 12-week core part:

- JIA ACR 50/70/90/100 proportion responders at week 12:  $\geq 3$  out of the 6 JIA core set variables with  $\geq 50/70/90/100\%$  improvement from baseline with no more than 1 of the remaining variables worsened by  $\geq 30\%$ ; [REDACTED]
- Juvenile Arthritis Disease Activity Score-27 (JADAS-27) change from baseline at Week 12

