***As observed including post discontinuation follow-up:***

All observed data up to week 12, including those collected after treatment discontinuation, will be included in the analysis. No missing data will be imputed.

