**2.4.6.2 Analyses of other efficacy endpoints**

JIA ACR30 core set variable scores and changes from baseline for each dose regimen cohort and weight group will be summarized by visit using means, standard errors, and corresponding 95% CIs. JIA ACR30 response using ESR instead of hs-CRP will be summarized using the same methods as described in the previous section.

JIA ACR50/70/90/100 responses will be summarized using the same methods as described above for JIA-ACR30.

Overall score and change from baseline in JADAS-27 will be summarized by visit (including number, mean, standard error, SD, median, minimum, and maximum) for each dose regimen cohort and weight group (if possible).

Proportions of patients with the low disease activity ( $JADAS-27 \leq 3.8$ ) and inactive disease activity ( $JADAS-27 \leq 1.0$ ) as defined based on JADAS-27 will be explored and summarized. The Kaplan-Meier plot for time to first onset of achieving low disease activity or achieving inactive disease will also be provided.

For the analyses of continuous endpoints including JIA ACR core set variables and JADAS-27, no data will be imputed and the analyses will be done based on data as observed while the patient remains on treatment.

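### Week 12 means for the JIA ACR components and JADAS-27 come only from children still on treatment, with no companion summary using the off-treatment data collected to Week 12

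*SAP*

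**What the plan says.** SAP 2.1.5.2 names two continuous core-phase endpoints: "the change from baseline at week 12 in the 6 individual JIA ACR components" and "Juvenile Arthritis Disease Activity Score-27 (JADAS-27) change from baseline at Week 12". The default in SAP 2.1.5 is that "all efficacy evaluations up to the closeout measurement will be included for analysis unless otherwise specified". SAP 2.4.6.2 then specifies otherwise for these endpoints: "no data will be imputed and the analyses will be done based on data as observed while the patient remains on treatment". It offers no alternative. Protocol 11.4.2.2 describes by-visit summaries for the same endpoints and states neither an on-treatment restriction nor an alternative.

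Follow-up does not end when treatment does. Protocol 1.1.2 has children who stop in the core phase keep attending "without treatment administration through Week 12 (as per Food and Drug Administration (FDA) guidelines for missing data"). Protocol 6.1 asks this of all three portions and covers every scheduled assessment except dosing.

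The ACR responses are handled differently. In SAP 2.4.6.1 the main ACR30 summary is on-treatment, but three further approaches follow: non-responder imputation, LOCF, and an as-observed version in which "All observed data up to week 12, including those collected after treatment discontinuation, will be included in the analysis". SAP 2.4.6.2 carries these methods over to ACR50/70/90/100 and to ACR30 based on ESR, but not to the continuous endpoints.

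**The concern.** A secondary objective is to describe efficacy in patients with pcJIA. An on-treatment mean describes improvement in those still on drug at Week 12, and remaining on drug can depend on how the child is doing. If stoppers differ from stayers, the Week 12 mean is not the mean for treated children, and the distortion can differ between regimens.

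The trial collects the values needed to examine this and gives a missing-data reason for doing so. For the continuous endpoints the SAP sets them aside without explanation. Description is the whole purpose of these tables, so it matters whom the mean describes.

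**Working it through.** No figure in the plan bears directly on this point, so the check is mainly of text, followed by an illustration of size.

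**1. What an early stopper contributes at Week 12.** The core set is assessed every two weeks from Week 2 to Week 12 (Protocol 1.2.1). SAP 2.5.4 moves a discontinuation visit to the next visit with a planned assessment. For an every-other-week child, EOT is two weeks after the last dose. A last dose at Week 4 therefore gives a Week 6 value and no on-treatment Week 12 value. If EOT falls after the Week 10 visit, the value lands on Week 12. For JADAS-27, Week 12 is the only post-baseline core visit (Protocol 9.4.2), so any core-phase discontinuation value maps there. Whether such a value counts as on treatment is not defined. The core treatment epoch in SAP 2.1.4 ends 13 days after the last every-other-week dose, whereas EOT is nominally at 14 days.

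**2. Approaches compared.**

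| Endpoint | On treatment | Non-responder | LOCF | As observed, with off-treatment data |
|---|---|---|---|---|
| ACR30, ESR-based ACR30, ACR50/70/90/100 | yes | yes | yes | yes |
| Six components (change) | yes | not applicable | no | no |
| JADAS-27 (change) | yes | not applicable | no | no |

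**3. Who stops before Week 12.**
- Linked to poor response: if a cohort is declared ineffective on 6-week data, all its children must stop (Protocol 6.1.2.3). Its on-treatment Week 12 cell could be empty, or hold only children already past Week 12. Children may also stop because they need prohibited therapy (Protocol 10.3.3), and lack of efficacy may be assessed after six weeks (Appendix C).
- Not necessarily linked: hypersensitivity, infection, liver, neutrophil or platelet findings, and pregnancy (Protocol 10.3.3).
- Not removed: children who miss ACR30 at Week 12. Investigators receive that result only after Visit 12 (Protocol 1.2.1, footnote j), so their Week 12 values stay in the means.

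**4. Illustration of size.** Let d be the share of treated children off treatment at Week 12, and D the mean improvement of stayers minus that of stoppers, in SD units. The all-treated mean is (1 - d) x stayers + d x stoppers, so

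bias of the on-treatment mean = d x D.

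Both inputs are assumptions. The largest d borrows 1 - 60/72 = 16.7% from the statement that "up to approximately 72 patients will be enrolled (to achieve approximately 60 evaluable patients"). That is an allowance for non-evaluable children, not a discontinuation rate.

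| d | D = -0.5 | D = 0 | D = +0.5 | D = +1.0 |
|---|---|---|---|---|
| 5% | -0.025 | 0 | +0.025 | +0.050 |
| 10% | -0.050 | 0 | +0.050 | +0.100 |
| 16.7% | -0.083 | 0 | +0.083 | +0.167 |

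The standard error of a mean is SD/sqrt(n): 0.408 SD at n = 6 and 0.236 SD at n = 18. The largest bias shown is below one standard error in either cell. If third-portion children are pooled in, a weight group at the selected regimen could reach 18 + 20 = 38, where the standard error is 1/sqrt(38) = 0.162 SD. The extreme of the range is then about one standard error.

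The chance that at least one child is off treatment is 1 - (1 - d)^n. Over the three values of d this is 60% to 96% at n = 18, and 26% to 67% at n = 6.

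**The case against.** The strongest reply is that efficacy is secondary and descriptive with no testing (SAP 2.4.6, 2.4.6.3), and that on-treatment response is a coherent target in a PK-led dose-finding study. The SAP also puts the on-treatment summary first for ACR30. That stands: it is a reason to keep the on-treatment table and not to demote it. It does not explain why only the continuous endpoints lack a companion.

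A reader might infer that stoppers vanish altogether and that their data go unused. The documents do not support that. Stoppers contribute to by-visit summaries up to discontinuation. Their off-treatment component values feed the as-observed ACR analyses. Change in hs-CRP is also a PD endpoint at Week 12 or EOT (SAP 2.1.8), summarised with no stated on-treatment limit. JADAS-27 may pick up a mapped discontinuation value.

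Denominators are partly covered too. JADAS-27 summaries report the number, and SAP 2.2 tabulates core-phase completion and discontinuation. Neither shows, for each component, how many treated children are missing from the Week 12 mean.

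**Conclusion.** The point holds as a gap and an internal inconsistency. The continuous endpoints have a single on-treatment analysis, off-treatment values to Week 12 are collected for missing-data reasons, and the ACR responses use them. The Week 12 means may be biased, plausibly towards larger improvement if early stopping is tied to poor response.

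Two stronger readings go too far.
- That mean improvement is overstated. The sign depends on who stops and why: safety stops need not be poor responders, and children given another biologic keep attending visits (Protocol 8.8.1), so their off-treatment values may reflect that therapy.
- That the overstatement is 9% to 20%. That range comes from 1/(f + (1 - f)s) - 1 with f = 60/72 and stoppers achieving s = 0.5 down to 0 of the stayers' improvement. It treats the whole non-evaluable allowance as early stopping. Protocol 4.3.2 ties the evaluable number to precision for PK and PK-PD, not to Week 12 efficacy retention.

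Under the assumed ranges the bias is -0.083 to +0.167 SD, below one standard error at 6 or 18 children. This is a modest reporting point, worth correcting because the data will already be in hand.

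**What to change.** In SAP 2.4.6.2, for the core phase:
- Keep the on-treatment summary as it is.
- Add an as-observed Week 12 summary of change in each component and in JADAS-27 that includes values collected after discontinuation, following the ACR30 version in SAP 2.4.6.1.
- In both, show by regimen and weight group how many treated children contribute and how many do not.
- State whether a JADAS-27 discontinuation value mapped to Week 12 counts as on treatment, and which value is used in the added summary when the child also has a Visit 12 assessment.

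The cost is a short SAP edit and one extra set of tables, with no new data collection. The drawback is that some off-treatment values will reflect other therapy, as in the existing ACR30 version, and the tables should say so.

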#### **2.4.6.3 Multiplicity issues**

No formal hypothesis testing will be performed.

## 2.4.8 Analysis of immunogenicity variables

### *ADA prevalence and titer*

The following summary will be provided based on the ADA population:

- Number (%) of patients with an ADA positive sample at baseline
  - Number (%) of neutralizing antibody
  - Number (%) of non-neutralizing antibody
  - The summary statistics (including number, median, Q1, Q3, minimum and maximum) of the titer for the baseline ADA positive patients
- Number (%) of patients with an ADA negative sample at baseline

### *ADA incidence and titer*

The following summary will be provided based on the ADA population during the TEAE period:

- Number (%) of ADA-negative patients
- Number (%) of ADA-positive patients
  - Number (%) of patients with neutralizing antibody
  - Number (%) of patients with non-neutralizing antibody
- Number (%) of treatment-emergent ADA-positive patients.
  - The summary statistics (including number, median, Q1, Q3, minimum, and maximum) of the peak post-baseline titer for treatment-emergent ADA-positive patients
- Number (%) of transient treatment-emergent ADA positive patients
  - Number (%) of neutralizing antibody
  - Number (%) of non-neutralizing antibody
- Number (%) of persistent treatment-emergent ADA positive patients
  - Number (%) of neutralizing antibody
  - Number (%) of neutralizing antibody
- Number (%) of treatment-boosted ADA positive patients.
  - Number (%) of patients with neutralizing antibody
  - Number (%) of patients with non-neutralizing antibody

In addition, number (%) of patients with ADA positive or negative response at each visit will be summarized by dose regimen cohort. Persistent and transient ADA responses may be investigated during the extension phase of the trial where multiple ADA assessments are available.

### ***ADA and PK***

By visit descriptive summary of serum concentration of sarilumab will be provided by ADA patient classification (positive or negative) for each dose regimen cohort.

Scatter plots of serum concentration versus visit will also be provided by ADA classification (positive or negative) and dose regimen cohort.

In addition to the summaries and plots described above, individual, spaghetti, and/or other plots of relevant PK, ADA, and efficacy data may be produced to aid in the visualization/interpretation of the data.

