11.4.3 Analyses of safety data

Safety data will be summarized descriptively. The summary of safety results will be presented by dose regimen. Further subdivision by weight group will be performed only for selected parameters given the small sample size. Additional methods including the approach to handle the dose-adjustment in safety analyses, safety analyses by time periods, and the exposure-adjusted analyses on safety events will be detailed in the statistical analysis plan.

The safety analysis will be based on the reported AEs and other safety information, such as clinical laboratory data, vital signs, etc. Safety and acceptability assessments (local tolerability) are the primary objectives of the extension parts of the studies (see [Section 9.3](#)).

All safety analyses will adhere to Sanofi “Guideline for the Analysis and Reporting of Safety Data from Clinical Trials.”

Observation period

The observation period will be divided into 5 epochs: Screening, Treatment in core period, Treatment in extension period, Follow-up, and Post-study (defined below):

- The **Screening** epoch is defined as the time from the signed informed consent date up to the time prior to the first dose of IMP.
- The **Core-treatment** epoch is defined as the time from the first dose of IMP to last dose in the core treatment phase + 13 days (or + 6 days for patients on weekly dosing), or first dose of IMP in the extension period for patients who enter the extension phase.
- The **Extension treatment** epoch is defined as the time from first dose of IMP in extension period to last dose of IMP in extension period + 13 days (or + 6 days for patients on weekly dosing). Only patients who enter the extension period have the **Extension treatment** epoch.
- The **Follow-up treatment** epoch is defined as the time from the EOT epoch (ie, the end of **core-treatment** epoch for patients not entering in the extension period; or the end of the **extension treatment** epoch for patients who enter the extension period) to last dose of IMP + 60 days.
- The **Post-study epoch** is defined as the time after the last dose of IMP + 60 days. The rationale of having “last dose of IMP + 60 days” as the end of **follow-up** epoch is to capture the events observed within approximately 5 half-lives of the last IMP.

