11.4.6 Analysis of immunogenicity variables

At each sample time, the result of the ADA assay will be categorized as either positive or negative, and in the case of a positive result will be further characterized as either neutralizing or non-neutralizing.

ADA-positive patient is defined as a patient with at least 1 treatment-emergent or treatment-boosted ADA-positive sample during the TEAE period, where

- Treatment-emergent ADA-positive patient is defined as a patient with non-positive assay (meaning negative or missing) response at baseline but with a positive assay response during the TEAE period
- Treatment-boosted ADA-positive patient is defined as a patient with a positive ADA assay response at baseline and with at least a 4-fold increase in titer compared to baseline during the TEAE period.

ADA-negative patient is defined as a patient without a treatment-emergent or treatment-boosted ADA-positive sample during the TEAE period.

ADA prevalence and titer

The following summary will be provided based on the ADA population:

- Number (%) of patients with an ADA-positive sample at baseline
 - Number (%) of neutralizing antibody
 - Number (%) of non-neutralizing antibody
 - The summary statistics (including number, median, Q1, Q3, minimum, and maximum) of the titer for the baseline ADA-positive patients
- Number (%) of patients with an ADA-negative sample at baseline.

ADA incidence and titer

The following summary will be provided based on the ADA population during the TEAE period:

- Number (%) of ADA-negative patients
- Number (%) of ADA-positive patients
 - Number (%) of patients with neutralizing antibody
 - Number (%) of patients with non-neutralizing antibody
- Number (%) of treatment-emergent ADA-positive patients
 - The summary statistics (including number, median, Q1, Q3, minimum, and maximum) of the peak post baseline titer for treatment-emergent ADA-positive patients
- Number (%) of treatment-boosted ADA-positive patients
 - Number (%) of patients with neutralizing antibody

- Number (%) of patients with non-neutralizing antibody.

In addition, number (%) of patients with ADA-positive or negative response at each visit will be summarized by dose.

ADA and PK

By visit descriptive summary of serum concentration of sarilumab will be provided by ADA patient classification (positive or negative) for each dose regimen.

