#### *Observation period*

The observation period will be divided into 5 epochs: SCREENING, TREATMENT in core period, TREATMENT in extension period, FOLLOW-UP, and POST-STUDY (defined as below):

- The SCREENING epoch is defined as the time from the signed informed consent date up to the time prior to first dose of IMP.
- The CORE TREATMENT epoch is defined as the time from first dose of IMP to last dose in core phase +13 days for patients on bi-weekly dosing or +6 days for patients on weekly dosing, or first dose of IMP in the extension period for patients who enter the extension.
- The EXTENSION TREATMENT epoch is defined as the time from first dose of IMP in extension period to last dose of IMP in extension period + 13 days for patients on bi-weekly dosing or +6 days for patients on weekly dosing. Only patients who enter the extension have the EXTENSION TREATMENT epoch.
- The FOLLOW-UP epoch is defined as the time from the end of TREATMENT epoch (ie, the end of CORE TREATMENT epoch for patients not entering in the extension period; or the end of EXTENSION TREATMENT epoch for patients who enter the extension period) to “last dose of IMP+60 days”.
- The POST-STUDY epoch is defined as the time after the “last dose of IMP+60 days”.

The entire treatment-emergent adverse event (TEAE) period includes the CORE TREATMENT, EXTENSION TREATMENT (only applicable for patients who enter the extension), and FOLLOW-UP epochs. The TEAE period for the core part includes CORE TREATMENT epoch for patients who enter the extension, and includes CORE TREATMENT and FOLLOW-UP epochs for patients not entering the extension.

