### 2.1.7 Immunogenicity endpoints

The ADA blood samples will be collected before injection during the same visit according to the schedules of sample collection and at or near the onset and completion of the occurrence of an SAE. Details can be found in Section 1.2 Study Flow Charts of the protocols [REDACTED]

At each sample time point, the result of an analyzed sample in the antidrug antibody (ADA) assay will be categorized as either positive or negative, and in the case of a positive result will be further characterized as either neutralizing or non-neutralizing.

**ADA positive patient** is defined as a patient with at least 1 treatment-emergent or treatment-boosted ADA positive sample during the TEAE period, where

- Treatment-emergent ADA positive patient is defined as a patient with non-positive assay (meaning negative or missing) response at baseline but with a positive assay response during the TEAE period.
- Treatment-boosted ADA positive patient is defined as a patient with a positive ADA assay response at baseline and with at least a 4-fold increase in titer compared to baseline during the TEAE period.

**ADA negative patient** is defined as a patient without a treatment-emergent or treatment-boosted ADA positive sample during the TEAE period.

A treatment-emergent positive response is further classified as persistent or transient.

- Persistent ADA Response: treatment-emergent ADA detected at 2 or more consecutive post-treatment sampling time points, where the first and last ADA positive samples are separated by a period of at least 16 weeks. Also persistent in the case where the last sample analyzed is positive, regardless of any other time points.
- Transient Response: A treatment-emergent response that is not considered persistent.

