#### **2.4.4 Analyses of pharmacokinetic variables**

Serum trough concentrations of functional sarilumab will be summarized using descriptive statistics (including number, arithmetic and geometric means, SD, standard error of the mean (SEM), CV (%), minimum, median, and maximum) by dose regimen cohort, overall and by weight group, for each visit. The samples will be considered non-eligible for these analyses if the previous dosing time is <11 days or >17 days before the sampling time for every other week regimens; <5 days or >9 days before the sampling time for every week regimens. Concentrations below the lower limit of quantification (LLOQ) will be set to zero for samples at predose (Week 0). Other concentrations below LLOQ will be replaced by LLOQ/2. Semi-log plots of concentration over time will also be provided (no value at time 0). Serum concentrations of

functional sarilumab will be summarized using the descriptive statistics mentioned above by immunogenicity status for each dose regimen cohort at each visit.

Listings of serum concentration will be provided for each individual patient including subject identification (ID), gender, age, first dose date, visit number, categorized time point (0 for trough level and 1 for pre-dose), date/time of previous dose, PK sampling date/time, duration since first dose (days), duration since previous dose (dd:hh), and serum concentration (mg/L).

All PK analyses will be performed using the PK population.

[REDACTED]

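### The sarilumab concentration tables by ADA status use an ever-positive patient label, so samples drawn before the first positive ADA result are counted as ADA-positive

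*SAP*

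**What the plan says.** The ADA and PK part of SAP 2.4.8 specifies the table as follows: "By visit descriptive summary of serum concentration of sarilumab will be provided by ADA patient classification (positive or negative) for each dose regimen cohort". The same split is used for the plots of concentration against visit. Protocol 11.4.6 plans the same summary: "By visit descriptive summary of serum concentration of sarilumab will be provided by ADA patient classification (positive or negative) for each dose regimen".

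The grouping variable comes from SAP 2.1.7, where an ADA-positive patient is "a patient with at least 1 treatment-emergent or treatment-boosted ADA positive sample during the TEAE period". Everyone else is ADA-negative. Protocol 11.4.6 defines it in the same way. On the window, SAP 2.1.4 (Observation period) says: "The entire treatment-emergent adverse event (TEAE) period includes the CORE TREATMENT, EXTENSION TREATMENT (only applicable for patients who enter the extension), and FOLLOW-UP epochs". Follow-up ends where the post-study epoch starts, and Protocol 11.4.3 says that this epoch "is defined as the time after the last dose of IMP + 60 days".

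SAP 2.4.4 also plans concentration summaries "by immunogenicity status for each dose regimen cohort at each visit", without defining a status that can change from visit to visit. The ADA incidence part of SAP 2.4.8 does count ADA results per visit ("number (%) of patients with ADA positive or negative response at each visit will be summarized by dose regimen cohort"), but nothing links those counts to concentrations. SAP 2.1.7 defines persistent and transient responses, but the PK tables do not use them.

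**The concern.** A label that can be earned at any time in the TEAE period depends on the future when it is applied to an early visit. A child whose first positive sample is at Week 120 appears in the ADA-positive column at Week 2 and at every visit after that, including all those at which no ADA had been found. If ADA reduces sarilumab concentration only once it is present, the positive column is then a mixture of unaffected and affected concentrations, and the difference between columns shrinks.

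These tables and plots are the only planned display of ADA against exposure that can be seen in the unredacted text. A reader who finds similar concentrations in the two columns at Week 12 or Week 24 could conclude that ADA hardly matters for exposure in children, when the similarity may come from the way the columns were formed.

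**Working it through.** **Participation, reproduced first.** Protocol 6.3.1 and SAP 1.1 give 166 and 106 weeks. Adding screening, core, extension and follow-up gives 4 + 12 + 144 + 6 = 166 for the dose-finding and second portions, and 4 + 12 + 84 + 6 = 106 for the third. Both figures are reproduced.

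**Length of the labelling window.** The last q2w dose is at Week 154, or Week 94 in the third portion (Protocol 1.1.2 and 1.2.2.3).
- Dose-finding and second portions: Day 154 × 7 + 1 = 1079. Adding 60 gives Day 1139, and 1138 / 365.25 = 3.12 years.
- Third portion: Day 94 × 7 + 1 = 659. Adding 60 gives Day 719, and 718 / 365.25 = 1.97 years.
- The end-of-study ADA sample at Week 162 falls on Day 1135, inside the window. Up to eight scheduled post-baseline ADA samples can therefore set the label: Weeks 12, 24, 48, 72, 96, 120, 156 and 162.

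**Concentrations drawn before the first positive sample.** For a Group A child in the first two portions who stays on one regimen, the scheduled post-dose PK samples (Protocol 9.1.1 and 1.2.2.1) are Days 3, 5, 8 and 12, then Weeks 2, 4, 8, 12, 24, 48, 72, 96, 120, 156 and 162. That makes 15.

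| First positive ADA sample | PK samples before it, of 15 |
|---|---|
| Week 12 | 7 |
| Week 24 | 8 |
| Week 48 | 9 |
| Week 96 | 11 |
| Week 156 | 13 |

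All 15 count as ADA-positive under the plan. By the same count, 5 of 13 samples precede Week 12 in Group B (sampling schedule 1) and 3 of 9 in the third portion.

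**Illustration of the dilution.** The documents give no ADA incidence, no time to first positive and no effect of ADA on concentration, so all of these are assumed. Let R be the true ratio of geometric mean concentrations (positive to negative) once ADA is present, taken as 1 before the first positive sample. Let f be the share of ever-positive children already positive at a visit. The ratio shown is then R^f.

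Three timings of the first positive sample were taken over Weeks 12, 24, 48, 72, 96, 120 and 156:
- early: 60, 20, 10, 5, 3, 1 and 1%;
- middle: 30, 25, 15, 10, 10, 5 and 5%;
- even: one seventh at each visit.

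With R = 0.50:

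| Visit | Early | Middle | Even |
|---|---|---|---|
| Week 12 | 0.5^0.60 = 0.66 | 0.5^0.30 = 0.81 | 0.5^(1/7) = 0.91 |
| Week 24 | 0.5^0.80 = 0.57 | 0.5^0.55 = 0.68 | 0.5^(2/7) = 0.82 |
| Week 48 | 0.5^0.90 = 0.54 | 0.5^0.70 = 0.62 | 0.5^(3/7) = 0.74 |
| Week 156 | 0.50 | 0.50 | 0.50 |

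The Week 12 range is 0.49 to 0.84 if R = 0.30, and 0.87 to 0.97 if R = 0.80. Across the 14 on-treatment PK samples, 56% (early) to 71% (even) of ever-positive children's concentrations precede the first positive sample. Counting from Week 12 only, the share is 11% to 43%.

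**After the change.** If each concentration is grouped by the status known at that visit, no concentration from before the first positive sample enters the positive group. Under the same assumptions the ratio shown from Week 12 onward is R itself.

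**The case against.** The strongest reply is that these are supportive, descriptive tables in a trial without hypothesis tests, and that several stronger conclusions do not follow. Much of this stands.

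- A reader might infer that the primary PK results are affected. They are not: Cmax, AUC and Ctrough are summarised by dose and weight group (SAP 2.4.4, Protocol 11.4.4), with no ADA split. An ADA effect on exposure is not a stated objective.
- A reader might infer that children who stop early are stuck in the negative group. The end-of-treatment and end-of-study visits both include ADA sampling (Protocol 10.1.10 and 10.1.11). These children have fewer chances to be found positive, but they are not fixed as negative.
- A reader might infer that dose selection rests on a three-year label. At the first interim analysis the label rests mainly on the Week 12 sample, so there is little or no dilution at Week 12 itself. The concentrations from Day 3 to Week 8 still carry a label set later.
- SAP 2.1.4 also defines a shorter TEAE period for the core part, and the ADA definition does not say which period applies. Under the shorter one, a Week 120 positive would not relabel the core visits. The final by-visit tables run through the extension, however, and even the core window labels Weeks 2 to 8 from a Week 12 result.
- The population PK covariates and part of SAP 2.4.4 are redacted, so a time-varying ADA term there cannot be excluded. That would not change these tables.

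The per-visit ADA counts and the optional individual plots help a careful reader, but neither corrects the split.

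The direction of the bias is also conditional. If low early exposure itself predisposes to ADA, concentrations from before conversion would show a difference that ADA did not cause. That too is a reason to separate concentrations before and after the first positive sample.

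**Conclusion.** The point holds for the descriptive ADA and PK tables and plots. By the plan's own definitions, concentrations from before the first positive ADA sample are reported as ADA-positive, and in Group A that includes all 7 scheduled post-dose samples before Week 12 for every ever-positive child. If ADA lowers exposure only once present, the contrast is pulled towards no difference, most at early visits and not at all by the last ADA visit.

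The size cannot be derived from the documents. A Week 12 ratio of about 0.66 to 0.91 in place of 0.50 illustrates the mechanism under an assumed halving and assumed timings; it is not an estimate for this trial. The change is a worthwhile, inexpensive improvement to a supportive analysis. Nothing here shows that the primary endpoint summaries are biased, and the handling of ADA in the population PK model cannot be judged from the redacted text.

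**What to change.** In SAP 2.4.4 and 2.4.8 and in Protocol 11.4.6:

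- From Week 12 onward, group each concentration by the ADA status known at that visit: treatment-emergent or treatment-boosted positive at or before the matched ADA sample, against not yet positive.
- Flag transient responders, or show them by the ADA result at that visit, so that a resolved response is not carried forward unmarked.
- Leave concentrations before Week 12 unsplit. No post-baseline ADA sample is scheduled in that interval, and borrowing the Week 12 result would again use a label from the future.
- Keep the ever-positive split as a secondary display, labelled as such.
- Define immunogenicity status in SAP 2.4.4 in the same terms, so that the two sections describe one analysis.

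No new sampling is needed, because ADA results per visit are already collected and counted. The cost is revised wording, one extra programming step, and small numbers in the positive group at early visits. The numbers will be smallest in the dose-finding cohorts, which plan 6 patients per regimen and weight group.
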